1. VERSION HISTORY

Table 1. Summary of Changes

Version/Date	Associated Protocol Amendment	Rationale	Specific Changes
1/ 28 May 2020	Protocol amendment 1 24 Mar 2020	Original version	N/A
2/ 21 January 2021	Protocol amendment 3 26 August 2020	
 Updated different sections to match the protocol amendment 3. Updated the healthcare utilization analysis per protocol amendment 3. Updated the multiplicity adjustment method per CBER feedback. 	
 Updated the wording of 2 exploratory objectives (in Section 2.1.3.1) and endpoints (in Section 3.3.1) to match the amended protocol. Updated the endpoint related to healthcare utilization (in Section 3.3.1) as well as Section 3.6 to match the amended protocol. Updated the period for collecting MA-RTIs (in Section 3.5.1) to match the updated protocol. Updated Section 3.5.2.1 to consistently use 2.0 cm instead of a mix of 2.0 and 2.5 (no change to the meaning of the text). Updated text (in Section 3.5.2) to clarify that only an investigator can classify a fever as Grade 4. Updated the evaluable infant population (in Section 4) to remove infants receiving extensive transfusions. Updated Section 5.1 to replace Hochberg multiplicity adjustment references with Bonferroni references per CBER feedback.

Table 1. Summary of Changes

Version/Date	Associated Protocol Amendment	Rationale	Specific Changes
			
 Updated Sections 6.3.1.10 and 6.3.2.2.1 to remove the 50% references regarding serum neutralizing titers in order to match updated protocol. Removed Appendix 1 Multiplicity Correction Strategy as it is no longer needed since the Bonferroni procedure will be used.
3/ 28 May 2021	Protocol amendment 4, 22 Mar 2021	
 Updated different sections to match protocol amendment 4. 	
 Added a new secondary objective (in Section 2.1.2.1) as per the amended protocol. Updated the endpoint related to the incidence of MA-LRTI due to RSV (in Section 2.1.3.1) to match the amended protocol. Added a new endpoint related to analyses in premature infants (in Section 2.1.3.1) as per the amended protocol. Added a new estimand for MA-LRTI due to RSV occurring up to 210 days, 240 days, 270 days, and 360 days (in Section 2.1.5.1) as per the amended protocol. Added clarification for sample size in Section 2.2 and a note for the adolescent maternal participants to match the amended protocol. Updated the 2 secondary endpoints to extend the timing of the analysis to 360 days after birth and added a new endpoint for MA-LRTI due to RSV after

Table 1. Summary of Changes

Version/Date	Associated Protocol Amendment	Rationale	Specific Changes
			
180 days and up to 360 days in Section 3.2.1 to match the amended protocol.
 
 • Updated the endpoint related to MA-LRTI due to RSV and added a new endpoint for premature infants to Section 3.3.1. • Added clarification throughout Section 3.5.2 about reaching out to the participant's parent(s)/legal guardian (if a minor). • Updated Section 6.1.3.1 and Section 6.1.3.2 to remove analyses that were not presented in other studies in the program. • Updated Section 6.2.1.1.1 to add the time point at 360 days. • Added Section 6.2.1.3 for the new secondary endpoint. • Updated Section 6.3.1.4 for the period of the analysis. • Updated to mention all time points included (120, 150, and 180 days) in Section 6.1.1.2.1, Section 6.2.1.1.1, and Section 6.3.1.1. • Added Section 6.3.1.13 for the analyses on premature babies. • Updated Table 10 by removing the efficacy subgroup analyses by time from vaccination to delivery, changing the population for the immunogenicity endpoints for the same

Table 1. Summary of Changes

Version/Date	Associated Protocol Amendment	Rationale	Specific Changes
			
subgroups, adding some clarification for the pregnancy outcome, adding new subgroup analyses by age at vaccination (to match the updated protocol), changing name of a subgroup from “time of enrollment” to “duration of planned follow-up” (same groups), and removing the groups for income-level subgroup analyses.
 
 • Updated Appendix 1 as AESI category is now collected in the CRF. • Updated Section 6.5.11 to add GA at vaccination categories in the demographic variables to be presented. • Updated Section 6.6.5 to add GA at birth categories. • Removed former Appendix 2 and added the URL for the source website in the reference section. • Removed 1 reference as it was only mentioned in an appendix that was deleted.
4/ 13 Oct 2021	Protocol amendment 4, 22 Mar 2021	
 • Updated different sections to make the exclusions endpoint specific. 	
 • Updated the primary and secondary estimands (in Section 2.1.4 and Section 2.1.5) related to intercurrent events to account for removing events that happen after an extreme transfusion or administration of palivizumab/another monoclonal antibody therapy targeting RSV.

Table 1. Summary of Changes

Version/Date	Associated Protocol Amendment	Rationale	Specific Changes
			
 • Updated Section 2.1.4.1 to specify that severe MA-LRTIs due to RSV positive adjudicated cases will be programmatically derived as MA-LRTI due to RSV. • Updated Section 4 to remove the reference to the data handling memo as a result of a process change. • Updated Section 4 to remove from the evaluable efficacy – infant population definition extreme transfusion and administration of palivizumab/another monoclonal antibody therapy targeting RSV (to make these exclusion endpoint-specific). • Updated Table 8 to explain that all severe MA-LRTIs due to RSV are a subset of MA-LRTI due to RSV. • Updated Section 6.1.1.1, Section 6.1.1.2.1, Section 6.2.1.1.1, Section 6.2.1.3.1, Section 6.3.1.1, Section 6.3.1.2, Section 6.3.1.8, and Section 6.3.1.13 in the analysis portion to specify that cases after extreme transfusion or administration of palivizumab/another monoclonal antibody therapy targeting RSV will be excluded.

Table 1. Summary of Changes

Version/Date	Associated Protocol Amendment	Rationale	Specific Changes
			
 • Updated Section 6.5.1.1 for the GA at vaccination categories to include a new category (“>36 weeks”) and revised the “≥ 32 to <36 weeks” category to “≥ 32 to ≤ 36 weeks” to include 36 weeks. • Removed the text on NDCMC-specific terms from Section 6.6.1 and added a reference regarding summary and listings data generation in Section 6.6.6 (as only 1 combined output with 2 different sources will be required). • Updated Section 6.3.1.9 to add more specifics for an analysis of non-RSV-positive pathogens only using RSV-positive adjudicated MA-LRTI cases. • Updated Table 10 to change the categories of the “Time since vaccination to delivery” variable, to combine the previous 2 categories. • Updated Table 10 to add subgroup analyses by gender and race as per CBER request. • Updated Section 6.6.3 to a flexible language as it is not sure these outputs will be required.

Table 1. Summary of Changes

Version/Date	Associated Protocol Amendment	Rationale	Specific Changes
			
 Updated Section 7.1 and Section 7.2 to allow the DMC members to look at severe cases at the interim analysis from a safety perspective.
5/31 Mar 2022	Protocol amendment 5, Jan 2022	
 Updated sensitivity/supplementary analysis per CBER request. Updated interim analysis section to follow PA5. 	
 Added Section 5.3.3 to describe management of missing data in efficacy analysis as per CBER request. Updated Section 6.1.1.1.2 to specify the analysis addressing the issue of missing swabs. Updated Section 6.2.1.1.2 with additional details for an analysis that was requested by CBER. Updated language in Section 7.2 to include the possibility of having 2 interim analyses and to specify the minimum number of cases for this analyses. Updated Section 7.2 with more details about alpha levels to be used for efficacy endpoints. Updated Table 11 to show examples for vaccine efficacy at both potential interim analyses (at 43 and 62 cases).
6/02 Sep 2022	Protocol amendment 7, 08 Aug 2022	
 Updated sensitivity/supplementary analysis per CBER request. Updated the interim analysis section to follow PA7. 	
 Removed the IgG1 endpoint from Section 3.3.2 as per PA7. Updated Section 5.3.2 to specify that some LLOQ values might not be in the table.

Table 1. Summary of Changes

Version/Date	Associated Protocol Amendment	Rationale	Specific Changes
			
 Updated Section 6.1.1.1.2 to include the expanded swab analysis, the imputed missing swab analysis, and the combined Phase 2 and 3 efficacy analysis. Updated Section 6.1.1.2.2 to add the imputed missing swab analysis and combined Phase 2 and 3 efficacy analysis. Updated Section 6.3.2.3 to remove all references to IgG1. Updated Section 6.4 to allow for the analysis of a subset of immunogenicity results. Updated Section 7.2 as per the updated protocol and CBER feedback. Updated Table 11 as per the updated protocol.

2. INTRODUCTION

This SAP provides the detailed methodology for summary and statistical analyses of the data collected in Study C3671008. A brief description of the study design and the study objectives is given below. Subsequent sections describe analysis populations and give the definitions of the endpoints, followed by details of statistical reporting. A list of tables, listings, and figures, mockup shells, and programming rules are prepared separately based on the methods described in this document. This document may modify the plans outlined in the protocol; however, any major modifications of the primary endpoint definition or its analysis will also be reflected in a protocol amendment.

2.1. Study Objectives, Endpoints, and Estimands

2.1.1. Primary Objectives

2.1.1.1. Primary Efficacy Objectives – Infant Participants

- To evaluate the efficacy of RSVpreF in reducing the incidence of MA-LRTI due to RSV.
- To evaluate the efficacy of RSVpreF in reducing the incidence of severe MA-LRTI due to RSV.

2.1.1.2. Primary Safety Objective – Infant Participants

- To describe the safety of RSVpreF.

2.1.1.3. Primary Safety Objective – Maternal Participants

- To describe the safety and tolerability of RSVpreF.

2.1.2. Secondary Objectives

2.1.2.1. Secondary Efficacy Objectives – Infant Participants

- To evaluate the efficacy of RSVpreF in reducing the incidence of hospitalization due to RSV.
- To evaluate the efficacy of RSVpreF in reducing the incidence of all-cause MA-LRTI.
- To evaluate the efficacy of RSVpreF in reducing the incidence of MA-LRTI due to RSV occurring within 360 days after birth.

2.1.3. Exploratory Objectives

2.1.3.1. Exploratory Objectives – Infant Participants

- To evaluate the efficacy of RSVpreF in reducing the incidence of MA-RTI due to RSV.
- To evaluate the efficacy of RSVpreF in reducing the incidence of MA-RTI.
- To evaluate the efficacy of RSVpreF in reducing the incidence of MA-LRTI due to RSV in infants after 12 months of age.
- To evaluate the efficacy of RSVpreF in reducing the incidence of severe MA-LRTI due to RSV in infants after 6 months of age.
- To evaluate the efficacy of RSVpreF in reducing the incidence of hospitalization due to RSV in infants after 6 months of age.
- To evaluate the efficacy of RSVpreF in reducing the incidence of all-cause MA-LRTI in infants after 6 months of age.

- To evaluate the efficacy of RSVpreF in reducing the incidence of MA-LRTIs due to RSV A and the incidence of MA-LRTIs due to RSV B.
- To describe the non-RSV infectious etiology of MA-RTI in the study population.
- To evaluate RSV serum neutralizing titers elicited by RSVpreF and transferred transplacentally.
- To assess the impact of RSVpreF on RSV illness based on socioeconomic factors.
- To assess the effect of RSVpreF on healthcare utilization.
- To describe the efficacy of RSVpreF in reducing the incidence of MA-RTI, MA-LRTI, and severe MA-LRTI in premature infants <37 weeks of age.

2.1.3.2. Exploratory Objectives – Maternal Participants

- To describe MA-RTI in this study population.
- To evaluate the immune responses elicited by RSVpreF.

2.1.4. Primary Estimands

2.1.4.1. Primary Efficacy Estimands – Infant Participants

- **VE, defined as the RR reduction of RSV-positive MA-LRTI occurring within 90 days, 120 days, 150 days, and 180 days after birth in the RSV vaccine group compared to the placebo group.**

This estimand includes the following 4 attributes:

- Population: Infant participants born to maternal participants receiving 1 dose of investigational product and in compliance with the key protocol criteria (evaluable efficacy infant participants).
- Variable: Occurrence of RSV-positive MA-LRTI within 90 days, 120 days, 150 days, and 180 days after birth as confirmed by the EAC (any adjudicated severe MA-LRTI cases due to RSV are also by definition MA-LRTI cases).
- Intercurrent event(s): For participants who discontinue from the study or have major protocol deviations, all postdiscontinuation or postviolation observations will be censored; such events include the infant receiving palivizumab or another monoclonal antibody targeting RSV and the infant receiving transfusions of more than 20 mL/kg of any blood products at ≤ 180 days of age.
- Population-level summary: RR reduction of RSV-positive MA-LRTI occurring up to 90 days, 120 days, 150 days, and 180 days in the RSV vaccine group compared to the placebo group.

- **VE, defined as the RR reduction of severe MA-LRTI due to RSV occurring within 90 days, 120 days, 150 days, and 180 days after birth in the RSV vaccine group compared to the placebo group.**

This estimand includes the following 4 attributes:

- Population: Infant participants born to maternal participants receiving 1 dose of investigational product and in compliance with the key protocol criteria (evaluable efficacy infant participants).
- Variable: Occurrence of severe MA-LRTI due to RSV occurring within 90 days, 120 days, 150 days, and 180 days after birth as confirmed by the EAC.
- Intercurrent event(s): For participants who discontinue from the study or have major protocol deviations, all postdiscontinuation or postviolation observations will be censored; such events include the infant receiving palivizumab or another monoclonal antibody targeting RSV and the infant receiving transfusions of more than 20 mL/kg of any blood products at ≤ 180 days of age.
- Population-level summary: RR reduction of severe MA-LRTI due to RSV occurring up to 90 days, 120 days, 150 days, and 180 days in the RSV vaccine group compared to the placebo group.

2.1.4.2. Primary Safety Estimands – Infant Participants

- **Percentage of infant participants with specific birth outcomes.**

This estimand includes the following 4 attributes:

- Population: Infant participants born to maternal participants receiving 1 dose of investigational product.
- Variable: Presence/absence of specific birth outcomes (see [Appendix 1](#)).
- Intercurrent event(s): No intercurrent events to be considered.
- Population-level summary: Percentage of infant participants with specific birth outcomes in each group.

- **Percentage of infant participants having AEs from birth to 1 month of age.**

This estimand includes the following 4 attributes:

- Population: Infant participants born to the maternal participants receiving 1 dose of investigational product.
- Variable: Presence/absence of AEs from birth to 1 month.

- Intercurrent event(s): For participants who discontinue, all collected data will be included; missing AE dates will be imputed as described in Pfizer's Vaccine Statistics Rulebook.
- Population-level summary: Percentage of infant participants with AEs from birth to 1 month of age in each group.
- **Percentage of infant participants with SAEs and NDCMCs from birth through 6 and 12 months.**

This estimand includes the following 4 attributes:

- Population: Infant participants born to the maternal participants receiving 1 dose of investigational product.
- Variable: Presence/absence of SAEs and NDCMCs from birth through 6 and 12 months of life.
- Intercurrent event(s): For participants who discontinue, all collected data will be included; missing AE dates will be imputed as described in Pfizer's Vaccine Statistics Rulebook.
- Population-level summary: Percentage of infant participants with the event of interest during the first 6 and 12 months of life in each group.
- **Percentage of infant participants with SAEs and NDCMCs from birth through 24 months.**

This estimand includes the following 4 attributes:

- Population: Infant participants born to the maternal participants enrolled during the first year of the study and who received 1 dose of investigational product.
- Variable: Presence/absence of SAEs and NDCMCs from birth through 24 months of life.
- Intercurrent event(s): For participants who discontinue, all collected data will be included; missing AE dates will be imputed as described in Pfizer's Vaccine Statistics Rulebook.
- Population-level summary: Percentage of infant participants with the event of interest during the first 24 months of life in each group and percentage of infant participants with the event of interest between 12 and 24 months of life in each group.

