3.5.5. Birth Outcome: Infant Participants

Infant outcome at birth will be collected at the delivery visit and includes the following: GA (weeks, days); Apgar score at 1, 5, and 10 minutes; infant cry immediately after delivery (yes, no); infant suckle shortly after delivery (yes, no); and infant outcome (normal, congenital malformation/anomaly, other neonatal problem or unknown). Neonatal death will be derived using the response to “delivery outcome” from the pregnancy outcome and the AE data. Neonatal death is defined as the death of a live-born infant that occurred within a month (30 days) after birth.

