6.1.2. Primary Safety Endpoints: Infant Participants**6.1.2.1. Specific Birth Outcomes**

- Analysis set: Safety – infant ([Section 4](#)).
- Analysis methodology: Descriptive summary statistics.
- Intercurrent events and missing data: Analysis will be carried regardless of whether an intercurrent event occurs.

- For each group, the number and proportion of participants with each specific birth outcome (see [Appendix 1](#) for the list of specific birth outcomes) will be presented by vaccine group. In addition, the difference in proportions and associated 2-sided 95% CI between the vaccine group and the placebo group will be presented.

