6.6.5. Birth Outcomes

Descriptive summaries and data listings will be generated for the birth outcomes. The summaries and listings for these data will be generated only for infant participants. In addition to the information collected in the CRF, the following groups will also be presented for the GA at birth: ≥ 24 and < 28 weeks, ≥ 28 to < 34 weeks, ≥ 34 to < 37 weeks, ≥ 37 to < 42 weeks, and ≥ 42 weeks.

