9. APPENDICES

Appendix 1. Specific Birth Outcomes

The specific birth outcomes of interest for this study are listed below:

- AEs categorized as AESIs in the database
- Neonatal death
- Congenital malformations/anomalies
- Other neonatal problems
- Final Apgar score (at either 1, 5, or 10 minutes) less than 7

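### No specific birth outcome is derived from recorded gestational age or birth weight, so the planned vaccine-placebo difference reflects preterm birth and low birth weight only as far as they are reported

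*SAP*

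**What the plan says.** SAP 2.1.4.2 sets the estimand summary as "Population-level summary: Percentage of infant participants with specific birth outcomes in each group" and points to Appendix 1 for the outcomes. Appendix 1 has five items:

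- "AEs categorized as AESIs in the database"
- death in the neonatal period
- congenital anomalies
- "Other neonatal problems"
- a final Apgar score below 7

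For these outcomes, 6.1.2.1 adds that "the difference in proportions and associated 2-sided 95% CI between the vaccine group and the placebo group will be presented".

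The measured data are described elsewhere. Section 3.5.5 has GA in weeks and days collected at the delivery visit. Section 3.5.3.2 has infant weight measured, and 3.4.1 makes the day of birth the baseline for the physical examination. In the reporting sections, 6.6.5 is a descriptive summary: "In addition to the information collected in the CRF, the following groups will also be presented for the GA at birth". It lists five bands, three of them below 37 weeks. Section 6.6.3 leaves physical-examination summaries optional and gives no weight category.

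**The concern.** Vaccination takes place during pregnancy; the subgroup table (Table 10) bands GA at vaccination from 24 to 36 weeks. Whether the vaccine shifts the timing of birth or birth weight is therefore a central infant-safety question. Both are measured in the study. The comparison that the plan commits to nevertheless uses reported categories and not these measurements. If sites do not report or categorise every preterm or low-weight birth, the planned difference understates any true difference, and its confidence limits move with it. If a preterm contrast is then wanted after unblinding, its definition and cut-off will be chosen with the data in view.

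**Working it through.** **Comparison of the sections.** The SAP gives no rate, sample size or power for birth outcomes, so there is no figure of its own to reproduce.

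| Source | Uses recorded GA or weight? | Difference with CI stated? |
|---|---|---|
| Appendix 1 with 6.1.2.1 | No, 0 of 5 items | Yes |
| 6.1.2.2, AEs within 1 month | No, reported preferred terms | Yes, for Tier 2 terms (at least 1% in a group, 3.5.1) |
| 6.6.5, GA at birth | Yes, five bands | No; no total below 37 weeks |
| 6.6.3, physical examination | Possibly weight | No; the summary itself is optional |

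Two features show that a derived outcome would fit the plan. Appendix 1 already accepts a measured threshold (Apgar below 7). The SAP also already uses the 37-week cut-off, in the exploratory efficacy analysis of 6.3.1.13.

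**Size of the loss from incomplete reporting.**

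Inputs:
- n = 3450 infants per arm, half of the 6900 pairs in SAP 2.2 (5000 per arm at the 10,000 maximum), taking one infant per mother.
- True preterm rates of 5% (placebo) and 6% (vaccine). This is an assumption; 4% vs 5% and 8% vs 9% are used as a range.
- Capture of 80% in both arms, in a row for a single reported term. This is an assumption.

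Formulas: SE = √[p₀(1−p₀)/n + p₁(1−p₁)/n]; z = (p₁−p₀)/SE; 95% half-width = 1.96 × SE.

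Recorded GA, 5% vs 6%:
- SE = √[(0.0475 + 0.0564)/3450] = 0.00549
- z = 0.0100/0.00549 = 1.82
- difference 1.00 ± 1.08 points

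80% capture, 4.0% vs 4.8%:
- SE = √[(0.0384 + 0.0457)/3450] = 0.00494
- z = 0.0080/0.00494 = 1.62
- difference 0.80 ± 0.97 points

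The expected upper confidence limit falls from 1.00 + 1.08 = 2.08 points to 0.80 + 0.97 = 1.77 points. Missed cases thus make the result look both smaller and more precise.

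Over the range, the same formulas give:

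| True rates | n per arm | z, recorded GA | z, 80% capture |
|---|---|---|---|
| 4% vs 5% | 3450 | 2.00 | 1.78 (3.2% vs 4.0%) |
| 5% vs 6% | 3450 | 1.82 | 1.62 (4.0% vs 4.8%) |
| 8% vs 9% | 3450 | 1.49 | 1.32 (6.4% vs 7.2%) |
| 5% vs 6% | 5000 | 2.19 | 1.95 (4.0% vs 4.8%) |

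Equal capture c in both arms multiplies the difference by c. At 90%, 70% and 50% capture, a 1-point excess appears as 0.90, 0.70 and 0.50 points.

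**The case against.** The case against is substantial, and most of it limits the point. Four stronger readings are tempting, and the SAP does not support them.

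- **Preterm birth can enter only through an AESI flag.** It cannot be shown. The other-neonatal-problems item is fed by a delivery-visit field (3.5.5) and needs no flag. The SAP also never says whether preterm birth or low birth weight is an AESI; 6.6.1 refers that definition partly to the protocol, which is not shown. Both routes are still reported categories.
- **Measured GA is never compared between arms.** This goes too far. Section 5.2 requires summaries by vaccine group, so the three bands below 37 weeks are visible by arm and can be added by hand. Section 5.2.1 allows a CI for a difference where appropriate. What is missing is a commitment to the total and its interval.
- **The signal is lost in one pooled AESI row.** The SAP does not say that all AESIs collapse into one row, and 6.6.1 plans a separate AESI summary. A preterm term reported as an AE in at least 1% of a group also gets its own Tier 2 difference in 6.1.2.2, and the assumed rates pass that threshold easily. The single-term row is therefore the fair comparison.
- **The flag is less complete for early births, because the version history says that the AESI category is now collected on the CRF.** A version history does not show that earlier births lack the flag or were not completed later.

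It is also fair to say that safety is descriptive here, that 6.6.1 treats it as exploratory, and that under the central assumption at 3450 per arm even recorded GA gives z below 1.96. None of this removes the core: where a difference is promised it rests on reporting, and where the measurement is shown no difference is promised.

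**Conclusion.** The point holds as an improvement to the plan, not as an error or contradiction in it. The difference promised in 6.1.2.1 uses no recorded GA or weight, the Tier 2 analysis rests on reported terms, GA bands carry no stated contrast, and no birth-weight summary is assured. The statistical loss is modest: about 0.2 in z (1.8 to 1.6) and 0.2 point in the estimated difference, for a 1-point excess on 5% with 80% capture and 3450 per arm. It grows in proportion as capture falls. The rates and the capture fraction are assumptions, and the SAP alone cannot show that reporting will be incomplete. The stronger argument is that the measured value is already in hand and makes the question of capture irrelevant.

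**What to change.** In Appendix 1 and 6.1.2.1, add two separate outcomes, derived from recorded data for every live-born infant in the infant safety set:

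- preterm birth: recorded GA at birth below 37 weeks, with the sub-bands of 6.6.5 shown beneath it
- low birth weight: recorded weight at birth, with a cut-off consistent with the protocol

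Report each with the difference in proportions and its 2-sided 95% CI, by the method in 5.2.1. Show the AESI categories on separate rows, so that the reported and derived counts can be compared. State the definitions before unblinding.

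The cost is a few lines of SAP text and a few table rows. No new data or procedures are needed, and the efficacy analyses and alpha allocation are not affected.
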